#### **4.5.8.6 Cutaneous Lupus Erythematosus Disease Area and Severity Index (CLASI)**

The CLASI is an instrument designed to capture SLE-specific mucocutaneous disease manifestations (see [Appendix 14](#)). It comprises a score for the activity of the disease and a score for the damage caused by the disease. The CLASI should be completed at intervals as indicated in the schedule of assessments for any patient who has mucocutaneous manifestations of SLE at a given study visit and at all subsequent visits. The CLASI will be used to capture mucocutaneous disease in any patient with mucocutaneous disease manifestations beginning on the visit that the mucocutaneous manifestation is first observed and periodically thereafter as outlined in the Schedule of Activities (see [Appendix 1](#)).

It is important that only SLE-specific lesions are included in this assessment. Training in the use of the CLASI will be available online and will be required for any new investigator from the beginning of Study GA30044.

#### **4.5.8.7 Physician's Global Assessment**

The Physician's Global Assessment (see [Appendix 15](#)) is a visual analog scale (VAS). Physicians are to rate the patient's disease activity over the past 28 days and place a vertical tick mark on a 100-mm analog scale from 0 to 3. The left-hand extreme of the

line is described as “None” and the right–hand extreme as “Severe.” Patient history, results of the physical examination, as well as pertinent laboratory values should be taken into account when rating the patient’s disease activity. Physicians should also refer to the value recorded at the previous visit and move the tick mark as appropriate.

#### **4.5.8.8 Patient’s Global Assessment**

The Patient’s Global Assessment is a VAS (see [Appendix 16](#)). The patient’s overall assessment of their current disease activity is measured using a vertical tick mark on a 100-mm VAS. The left-hand extreme of the line is described as “None” and the right–hand extreme as “Maximum.”

#### **4.5.8.9 Systemic Lupus Erythematosus Responder Index**

The SRI is a categorical assessment that evaluates disease activity in SLE based on the different organ systems. This index utilizes a combined evaluation of the SLEDAI-2K, BILAG, and Physician Global Assessment to measure response to treatment (see Sections [4.5.8.2](#), [4.5.8.1](#); [4.5.8.7](#)). The SRI-4 primary endpoint defines response as meeting all of the following criteria at Week 48 compared with baseline:

- $\geq 4$  point reduction in SLEDAI-2K score
- No new BILAG A organ domain score or 2 new BILAG B organ domain scores
- No worsening (worsening defined as a  $> 0.3$  point increase) in the Physician’s Global Assessment.

#### **4.5.8.10 BICLA**

The BICLA is a composite index that was originally derived by expert consensus of disease activity indices ([Wallace et al. 2011](#)). BICLA response is defined as *follows*:

- At least one gradation of improvement in baseline BILAG scores in all body systems with moderate or severe disease activity at entry (e.g., all A (severe disease) scores falling to B (moderate), C (mild), or D (no activity) and all B scores falling to C or D
- No new BILAG A or more than one new BILAG B scores
- No worsening of total SLEDAI-2K score from baseline
- No significant deterioration ( $\leq 10\%$ ) in physician’s global assessment, and
- No treatment failure (initiation of non-protocol treatment)

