## **PROTOCOL AMENDMENT, VERSION 3: RATIONALE**

Changes to the protocol, along with a rationale for each change, are summarized as follows and are reflected as applicable in the protocol:

- The Medical Monitor has been updated.
- The study design figure has been modified without changes to the overall design (Figure 1).
- The British Isles Lupus Activity Group (BILAG) and Physician's Global Assessment (PGA) components of the SRI-4 have been removed from the secondary endpoints because those components are not standalone endpoints. The reduction of at least 4 points from baseline in the Systemic Lupus Erythematosus Disease Activity Index (SLEDAI)-2K remains an exploratory endpoint because it is the only component within the SRI-4 that shows clinical improvement (Section 2).
- The endpoint to evaluate SRI-4 response at Week 48 with and without oral corticosteroid (OCS) taper to evaluate patients with high plasmablast signature levels to have an enhanced clinical response to GDC-0853 relative to patients with low levels remains a secondary endpoint. The other corresponding endpoints to evaluate SRI-4 response at Week 24 with and without OCS taper have been re-categorized as exploratory endpoints (Section 2, Section 6.4.2, and Section 6.4.3).
- To better characterize the progression of lupus in patients on trial and provide other endpoints that may be less sensitive to placebo response, the BILAG-based Composite Lupus Assessment (BICLA) and SRI-6 endpoints have been re-categorized from exploratory to secondary endpoints (Section 2).
- Pharmacokinetic (PK) objectives and endpoints have been updated to clarify that the stated analysis will be conducted solely on pharmacokinetic data generated from the current study. PK analyses that incorporate data from multiple clinical studies (potentially including GS39684), including population PK analyses using models that incorporate pooled data, may be conducted separately (Section 2).
- The length of the study has been updated from 62 to 61 weeks to reflect the sum of the 5-week screening period, 48-week study conduct period, and 8-week safety follow-up period (Section 3.2.1).
- Language has been added to clarify the reference for nonclinical efficacy data for the BTK inhibitor GDC-0834 (Section 3.3.1).
- The minimum SLEDAI-2K score requirement for subjects to enroll in the study has been increased from a 6 to an 8 to ensure severity of lupus is appropriate for the study (Section 4.1.1).

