#### **4.1.1 Inclusion Criteria**

Patients must meet all of the following criteria for study entry:

- Signed Informed Consent Form
- Age 18–75 years, inclusive
- Able to comply with the study protocol
- Fulfillment of SLE classification criteria according to either the current American College of Rheumatology (ACR) or Systemic Lupus International Collaborating Clinics (SLICC) criteria at any time prior to or at screening (see Appendix 5 and Appendix 6, respectively)
- At least one serologic marker of SLE at screening as follows:
  - Positive antinuclear antibody (ANA) test by immunofluorescent assay with titer  $\geq 1:80$ ; OR
  - Positive anti-double-stranded DNA (anti-dsDNA) antibodies; OR

- Positive anti-Smith antibody
- At both screening and Day 1, moderate to severe active SLE, defined as meeting all of the following unless indicated otherwise:
  - SLEDAI-2K score  $\geq 8$  (at screening only) with clinical SLEDAI-2K score  $\geq 4.0$  (at both screening and Day 1) (see [Appendix 10](#))
  - Physician’s Global Assessment  $\geq 1.0$  (out of 3) (see [Appendix 15](#))
  - Currently receiving at least one standard oral treatment (*e.g.*, corticosteroids, anti-malarials, and/or immunosuppressants) for SLE within the dose ranges, as specified below (see [Appendix 18](#)):
    - If on an OCS, the dose must be  $\leq 40$  mg/day prednisone (or equivalent, see [Appendix 18](#)) and must have been stable for at least 2 weeks prior to screening as well as during screening
    - If on anti-malarial or *immunosuppressant* therapies, may only be receiving medications from the following list within the specified dose range; dose and route of administration must be stable for 8 weeks prior to screening as well as during screening:
      - Azathioprine: 1 to 2.5 mg/kg/day
      - Methotrexate: 7.5 to 25 mg/week
      - Mycophenolate mofetil: 500 to 3000 mg/day
      - Mycophenolic sodium: 360 to 2160 mg/day
      - Hydroxychloroquine: 200 to 400 mg/day
      - Chloroquine: 100 to 250 mg/day
      - Quinacrine: 100 to 200 mg/day
      - Other: Consult with Medical Monitor

Note: Any combination of azathioprine, methotrexate, mycophenolate mofetil, or mycophenolic sodium is prohibited.

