## **6. STATISTICAL CONSIDERATIONS AND ANALYSIS PLAN**

Details of all statistical methods (including scoring of disease-activity or PRO instruments and missing data handling) will be provided in the Data Analysis Plan (DAP).

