## 6.4 EFFICACY ANALYSES

Efficacy analysis will be conducted for the intent-to-treat population, defined as all randomly allocated patients. Sensitivity analyses of additional study population (e.g., completers, *or* per protocol [excluding major protocol violators]) may also be performed *for the primary endpoint or key secondary endpoints* and will be detailed in the DAP. Biomarker-defined subgroup analyses will also be performed to identify subsets of patients who derive enhanced clinical benefit from GDC-0583. The focus of the subgroup efficacy analyses is on, but not limited to, subgroups defined by plasmablast signature levels.

Statistical tests will be conducted at the 0.05 significance level for the intent-to-treat (ITT) population and at the 0.20 significance level for plasmablast-signature defined subgroups. No multiplicity adjustments will be made to control the overall Type I error, and positive tests will be viewed as hypothesis generating rather than confirmatory.

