### 6.4.2 Secondary Efficacy Endpoints

The secondary efficacy endpoints *for this study* are as follows:

- *SRI-4 response at Week 48 with a sustained reduction of OCS dose to < 10 mg/day and ≤ Day 1 dose during Week 36 through Week 48*
- *SRI-4 response at Week 24 with a sustained reduction of OCS dose to < 10 mg/day and ≤ Day 1 dose during Week 12 through Week 24*
- *SRI-4 response at Week 24*
- *SRI-6 response at Weeks 24 and 48*
- *BICLA response at Weeks 24 and 48*
- *SRI-4 response at Week 48 in patients with high plasmablast signature levels relative to patients with low levels*
- *SRI-4 response at Week 48 with a sustained reduction of OCS dose to < 10 mg/day and ≤ Day 1 dose during Week 36 through Week 48 in patients with high plasmablast signature levels relative to patients with low levels*

*The secondary endpoints will be analyzed in the same fashion as the primary endpoint.*

*Further details for the secondary efficacy analyses will be specified in the DAP.*

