## **Appendix 3 Pre-Enrollment Adjudication**

Enrollment into this trial is subject to adjudication by the Sponsor's Medical Monitor or designated staff.

The purpose of the adjudication process is to ensure that clinical manifestations qualifying the patient for entry to the study (i) are adequately documented, (ii) are attributable to SLE, and (iii) are of sufficient severity to mandate significant immunomodulatory therapy.

The Medical Monitor will make the final decision regarding whether or not a patient is eligible for enrollment. Every effort will be made to complete the adjudication process as quickly as possible. In exceptional circumstances the screening period may, at the Medical Monitor's discretion, be extended to allow for completion of the adjudication process.

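### Does BICLA need a printed rule for patients with no BILAG A or B score at baseline?

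*Combined protocol and SAP*

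**What the plan says.** Section 4.5.8.10 defines BICLA response by five items. Only the first asks for improvement: "At least one gradation of improvement in baseline BILAG scores in all body systems with moderate or severe disease activity at entry", where A is glossed as severe and B as moderate. The other four bar new BILAG activity (any new A, or more than one new B), a rise in total SLEDAI-2K, deterioration in the Physician's Global Assessment (PGA), and treatment failure.

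Section 4.1.1 sets entry by SLEDAI-2K (total of at least 8 at screening only; clinical score of at least 4 at screening and Day 1), PGA of at least 1.0 and background oral treatment. It names no BILAG grade. Appendix 3 has the Medical Monitor confirm that manifestations "are of sufficient severity to mandate significant immunomodulatory therapy", again without a BILAG grade.

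On analysis, Section 6.4 says "Efficacy analysis will be conducted for the intent-to-treat population, defined as all randomly allocated patients". Section 6.4.2 treats the secondary endpoints like the primary one and adds: "Further details for the secondary efficacy analyses will be specified in the DAP". Section 6 gives the DAP all statistical methods, "including scoring of disease-activity or PRO instruments and missing data handling".

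**The concern.** A patient with no A or B on Day 1 has no body system to which the improvement item applies. Taken as a logical statement about all affected systems, the item is then met by default. What remains is close to SRI-4 (Section 4.5.8.9) with its improvement requirement removed. SRI-4 has the same limit on new activity, "No new BILAG A organ domain score or 2 new BILAG B organ domain scores", and a similar PGA limit, but it also demands a SLEDAI-2K fall of at least 4 points. BICLA asks only that the total not rise.

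That sits badly with the reason the Version 3 rationale gives for making BICLA and SRI-6 secondary, which was partly to "provide other endpoints that may be less sensitive to placebo response". Patients counted as responders without improving would raise the placebo rate. The words also bear the opposite reading: no gradation of improvement was shown, so the patient is a non-responder. The reported rates would depend on a choice that Section 4.5.8.10 leaves open.

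**Working it through.** **The plan's own figures.** None is given for BICLA. The design figure in Section 6.1 is for Week 48 SRI-4: about 88% power, 80 per arm, 50% against 75%, two-sided 0.05. Exact enumeration of Fisher's test gives 88.3%, so it reproduces. It does not depend on BICLA scoring.

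**Does the definition behave as feared?** Applied literally to a patient graded C, C, D at baseline:
- nothing changes: responder;
- one new B appears, all else unchanged: still a responder.

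By contrast, a patient whose single B stays B is a non-responder. The literal reading does what the concern says.

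**Can such a patient enter?** Two routes reach the SLEDAI-2K thresholds through Appendix 10:
- arthritis 4 + low complement 2 + increased DNA binding 2 = 8, clinical part 4;
- alopecia 2 + mucosal ulcers 2 + low complement 2 + increased DNA binding 2 = 8, clinical part 4.

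The Appendix 9 glossary has mild categories for arthritis, mucosal ulceration and alopecia. Its moderate arthritis category, however, needs only one joint with synovitis and some loss of movement. The conversion from items to grades is not in the text available, so these patients are plausible but not demonstrated.

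**Effect on each arm's rate.** Let f be the share with no A or B on Day 1, and q the share of those who do not worsen and have no treatment failure. Neither is in the documents. The two scorings differ by f × q (percentage points):

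| f | q = 60% | q = 80% | q = 90% |
|---|---|---|---|
| 2% | 1.2 | 1.6 | 1.8 |
| 5% | 3.0 | 4.0 | 4.5 |
| 10% | 6.0 | 8.0 | 9.0 |

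Not all of these patients lack improvement. If the planned 50% placebo SRI-4 rate held among them, those counted without an SRI-4 response are f × (q − 0.5), from 0.02 × 0.10 = 0.2 points to 0.10 × 0.40 = 4 points.

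With an assumed placebo rate e = 30% in patients who have an A or B, and q = 80%:
- f = 10%: default responder 0.90 × 0.30 + 0.10 × 0.80 = 35%; non-responder 0.90 × 0.30 = 27%; left out 30%.
- f = 2%: 31%, 29.4% and 30%.

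**Effect on the comparison.** With subscripts A for active and P for placebo:
- default responder: (1 − f)(eA − eP) + f(qA − qP);
- non-responder: (1 − f)(eA − eP).

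They differ by f(qA − qP), which is zero when q is equal across arms. If q differed by 20 points (assumed), the shift is 0.02 × 20 = 0.4 points or 0.10 × 20 = 2 points. With 80 per arm and 30% in both arms (assumed), the 95% half-width is 1.96 × √(2 × 0.30 × 0.70 / 80) = 14.2 points.

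**The case for a change.** The strongest case for a change is that Section 4.5.8.10 prints a complete responder definition, so its gap belongs there. Programmed as written, it would make these patients responders without anyone having chosen that. BICLA is read at Week 24 too, and unblinded interim review is planned once Week 24 SRI-4 evaluations are in. A fix needs no new data: BILAG is collected on Day 1, and a subset fixed before treatment keeps the protection of randomisation.

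Leaving these patients out could also recover some dilution. Borrowing 50% and 75% for patients with an A or B, f = 10%, q = 60% to 80% in both arms, and the pooled normal approximation without continuity correction:
- default scoring: difference 22.5 points, power 84% to 85%;
- non-responder scoring: difference 22.5 points, power 82.5%;
- restriction to 72 per arm: difference 25 points, power 88%.

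What stands is that the protocol text is silent and the two readings give opposite results for the same patient. The rest is weaker. The dilution is common to both scorings, so choosing between them does not remove it. Restriction changes the population being estimated and departs from the all-randomised analysis in Section 6.4; the baseline-restricted endpoints in Section 6.4.3 are exploratory. The statement that BICLA is easier than SRI-4 takes the 10% PGA limit as 0.3 on the 0 to 3 scale. As a share of a baseline of 1.0 it would be 0.1, stricter than SRI-4's 0.3. Finally, the default reading is not the obvious one, since the item opens by requiring a gradation of improvement.

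**Conclusion.** No change to the plan follows. This is a missing scoring detail for an uncommon type of patient, in a protocol that assigns instrument scoring and secondary-endpoint detail to the DAP. The analysts can be expected to settle it there, and the rule may already exist. Counting such patients as non-responders, or leaving them out with the other treatment as a sensitivity analysis, would each be defensible.

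The stakes are limited. The choice between the two all-randomised scorings moves rate levels by 1.2 to 9 points over the assumed ranges (f of 2% to 10%, q of 60% to 90%). The arm difference moves by nothing if q is equal across arms, and by at most 2 points in the unequal case tried. BICLA is one of several secondary endpoints tested without multiplicity adjustment, and Section 6.4 treats positive tests as hypothesis generating. SRI-4 at Week 48 is untouched.

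This rests on f being small. The documents do not give it, but an entry population described as moderate to severe, and adjudication on severity, both point that way. It also rests on the DAP fixing the rule before any unblinded efficacy review.

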#### **4.5.8.11 Optional Photography (*for United States only, as applicable*)**

For patients with cutaneous manifestations of SLE, optional photographs of the affected areas may be taken to document change over time while the patient is receiving study treatment. Photography is an optional assessment for patients (*United States only, as applicable*) who sign the optional photography consent and is contingent on EC/IRB approval.

#### **4.5.9 Laboratory, Biomarker, and Other Biological Samples**

Laboratory assessments will be performed as indicated on the Schedule of Activities (see [Appendix 1](#) and [Appendix 2](#)). All laboratory tests will be sent to one or more central laboratories for analysis, with the exception of serum and urine pregnancy tests, and erythrocyte sedimentation rate (ESR), which will be conducted locally.

At clinic visits at which study drug will be administered, laboratory samples should generally be drawn before the administration of study drug and after the administration of PRO assessments. An exception is on Week 24, where indicated PK samples should be collected prior to dosing and at timepoints also following study treatment administration (see [Appendix 1](#) and [Appendix 2](#)).

Samples for the following laboratory tests will be sent to the study site's local laboratory for analysis:

- ESR: Can be performed at local laboratory or as point of care test in clinic. The kits to perform the test will be provided by the central laboratory.
- Pregnancy test
  - All women of childbearing potential (including those who have had a tubal ligation) will have a serum pregnancy test at screening. Urine pregnancy tests will be performed at specified subsequent visits. If a urine pregnancy test is positive, it must be confirmed by a serum pregnancy test. Should a positive result be recorded at any time, the procedures detailed in Section [5.4.3](#) should be followed.
- Direct Coombs Test: Will be performed at a local laboratory per the SOA and should also be tested if the patient develops anemia that may be autoimmune in etiology.
- T-SPOT® Test for tuberculosis: may be performed at a local laboratory (optional)

Samples for the following laboratory tests will be sent to one or several central laboratories for analysis:

- Anti-dsDNA
- Anti-nuclear antibody test (immunofluorescence assay)
- Autoantibody panel: anti-Smith, anti-RNP, anti-Ro, anti-La, anti-cardiolipin, and anti-B2 glycoprotein
- C3, C4, and CH50
- Chemistry panel (serum or plasma): electrolytes (Na, K, Cl, bicarbonate, phosphorus), urea, creatinine, glucose, ALT, AST, amylase, lipase, total and direct bilirubin, ALP, GGT, albumin, globulin, total protein, calcium, uric acid
- Creatinine kinase (CK), aldolase, and lactate dehydrogenase (LDH)
- Coagulation panel: international normalized ration (INR), activated partial thromboplastin time (aPTT), prothrombin time (PT)

- High sensitivity C-reactive protein
- Fasting Lipids: Triglycerides, high-protein lipoprotein (HDL), low-density lipoprotein (LDL), hemoglobin A1c (HbA1c), and total cholesterol
- Hematology: hemoglobin, hematocrit, red blood cell (RBC) count, calculated indices (mean corpuscular volume [MCV], mean corpuscular hemoglobin [MCH], mean corpuscular hemoglobin concentration [MCHC], red cell distribution width [RDW]), platelets, WBC with differential
- Immunology: total immunoglobulins, IgG, IgM, IgE, and IgA
- TBNKs: Once treatment with study medication begins, TBNK results will be blinded.
- Urinalysis: dipstick (blood, protein, glucose, nitrites, and leukocyte esterase), microscopic analysis (RBC, WBC, red cell casts, white cell casts, *epithelial cells*)
- Viral serology
  - Hepatitis B: HBsAg, total HBcAb, and Hepatitis B surface antibody (HBsAb)
  - Hepatitis C (HCV) antibody
- QuantiFERON TB-Gold® (QFT); if QFT not available, a PPD skin test will be administered (see Section 4.5.7)

The following samples will be sent to the Sponsor or a designee for analysis:

- Plasma samples for PK analysis and metabolite identification, as needed.
- Plasma, serum, whole blood, urine, and RNA from blood for exploratory non-heritable PD markers potentially related to disease, drug, or clinical response; see Table 3.
- Whole blood for DNA extraction for exploratory research on inherited biomarkers (including, but not limited to, genes that express proteins which may influence GDC-0853 pharmacokinetics)

**Table 3 Proposed Biomarkers for Exploratory Research**

Sample Type	Timing	Proposed Biomarkers
Plasma	Baseline and subsequent timepoints during and after treatment	
 
• Markers including but not limited to: CCL3, CCL4
 

Serum	Baseline and subsequent timepoints during and after treatment	
 
• Markers including but not limited to: CXCL13, CCL20, and autoantibodies
 

Whole blood for FACS	Baseline and subsequent timepoints during and after treatment	
 
• Cells including but not limited to basophils and plasmablasts
 

RNA extracted from blood	Baseline and subsequent timepoints during and after treatment	
 
• Markers including but not limited to the plasmablast signature
 

Blood for peripheral blood mononuclear cells for CyTOF analysis	Baseline and subsequent timepoints during and after treatment	
 
• Cells and surface or activation markers, including but not limited to B and T cell subsets
 

Blood for peripheral blood mononuclear cells lysate	Baseline and subsequent timepoints during and after treatment	
 
• Markers including but not limited to phosphorylated and total BTK protein
 

Urine	Baseline and subsequent timepoints during and after treatment	
 
• Urinary biomarkers including but not limited to CXCL13, TWEAK, BAFF and lipids
 

BAFF = anti-B-cell activating factor; BTK = bruton's tyrosine kinase; CyTOF = cytometry by time of flight; FACS = fluorescence-activated cell sorting; TNF = tumor necrosis factor; TWEAK = TNF-like weak inducer of apoptosis.

For sampling procedures, storage conditions, and shipment instructions, see the laboratory manual.

Unless the patient gives specific consent for his or her leftover samples to be stored for optional exploratory research (see Section 4.5.13), biological samples will be destroyed when the final Clinical Study Report has been completed, with the following exception:

- Plasma samples collected for PK analysis will be destroyed no later than 5 years after the final Clinical Study Report has been completed.
- Blood, plasma, serum, and urine samples collected for biomarker analyses will be destroyed no later than 15 years after the final clinical study report (CSR) has been completed.

When a patient withdraws from the study, samples collected prior to the date of withdrawal may still be analyzed, unless the patient specifically requests that the samples be destroyed or local laws require destruction of the samples.

Data arising from sample analysis, including data on germline mutations, will be subject to the confidentiality standards described in Section 8.4.

